### **8.4.2 Primary Analysis (or Analysis of Primary Endpoints)**

Rate of completion of all adjuvant immunotherapy is defined as completion of all post-chemoradiation cycles of nivolumab, per protocol.

### **8.4.3 Secondary Analysis (or Analysis of Secondary Endpoints)**

**Objective Response Rate (ORR):** The ORR is based on the best overall response (BOR) recorded from the first day of treatment until time of assessment. The frequency and percentages of patients with a best overall response rate of complete response (CR), partial response (PR), stable disease (SD), or progressive disease (PD) will be determined.

**Locoregional Control (LRC) Rate:** Duration of LRC will be calculated as 1+ the number of days from the first day of treatment to time of documented locoregional clinical or radiographic relapse, progression or death due to any cause. For patients who continue treatment post-progression, the date of clinical or radiographic relapse or progression will be used for analysis. The Kaplan-Meier analysis will be used to calculate the mean LRC rate with 95% confidence interval.

**Distant Metastasis (DM) Rate:** Time to DM will be calculated as 1+ the number of days from the first day of treatment to documented clinical or radiographic progression at a distant metastatic site, or death due to any cause. Pathologic confirmation is not required to document the date of distant progression. For patients who continue treatment post-progression, the date of clinical or radiographic progression will be used for analysis. The Kaplan-Meier analysis will be used to calculate the mean DM rate with 95% confidence interval.

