### **2.2 Secondary**

- To determine the clinical response as judged by the investigator;
- To determine the overall response rate at 1 year from completion of therapy, as determined by RECIST 1.1 criteria;
- To determine the locoregional control rate at 1 year post-treatment;
- To determine the distant metastasis rate at 1 year post-treatment;
- ;
- To determine the rate of EBV DNA clearance at end of chemoradiation and at 1 year post-treatment;
- To determine the acute and late toxicity rates according to CTCAE v5.0, including immune-related adverse events (AEs);
- To assess patients' quality of life from baseline through 1 year post-treatment

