## 2.4.2 Secondary Endpoints

- ORR determined by investigator's assessment and RECIST 1.1 criteria;
- Locoregional control rate;
- Distant metastasis rate;
- Rate of EBV DNA clearance from plasma by standardized PCR assay;
- Treatment-emergent AEs and laboratory abnormalities as determined by National Cancer Institute Common Toxicity Criteria (NCI-CTC) version 4.0 and modified immune related criteria;
- Quality of life as assessed by patient reported outcomes (FACT-NP, FACT-Taxane, HHIE-S, and EuroQOL EQ-5D).

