#### 8.1.2 Secondary Endpoints

**Efficacy:** ORR as assessed by the study investigator by RECIST 1.1 criteria. The ORR is defined as the best overall response (BOR) recorded from the first day of treatment until time of assessment.

**Safety and tolerability:** Evaluate the number and frequency of Adverse Events (AEs) as determined by National Cancer Institute Common Toxicity Criteria (NCI-CTC) version 4.0 by investigator assessment.

- To determine the clinical response as judged by the investigator;
- To determine the overall response rate from the first day of treatment to 1 year post-treatment, as determined by RECIST 1.1 criteria;
- To determine the locoregional control rate at 1 year post-treatment;
- To determine the distant metastasis rate at 1 year post-treatment;
- ;
- To determine the rate of EBV DNA clearance at end of chemoradiation and at 1 year post-treatment;  
To determine the acute and late toxicity rates according to CTCAE v5.0, including immune-related adverse events (AEs);
- To assess patients' quality of life from baseline through 1 year post-treatment;

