### 8.2.2 Run-in phase

Six patients will be enrolled for the initial run-in phase, with nivolumab dosing of 240 mg. Enrollment will cease until all 6 patients have completed concurrent chemoradiation and nivolumab. If 3 or more of the first 6 patients experience grade 3-4 immune related toxicity or other DLT during concurrent chemoradiation and nivolumab therapy, then the run-in will restart at dose schedule 2 with 6 additional patients. In dose schedule 2, patients will start nivolumab

concurrent with chemoradiation and will not start nivolumab prior to chemoradiation. If 3 or more of the first 6 patients experience grade 3-4 immune related toxicity or other DLT during concurrent chemoradiation and nivolumab at dose schedule 2, then the dose schedule will be changed to dose schedule 3 and the run-in will restart at dose schedule 3 with 6 additional patients. In dose schedule 3, patients will start nivolumab in the adjuvant phase only and will not receive nivolumab before or during chemoradiation, and the toxicity of nivolumab will be assessed during the adjuvant phase. No dose escalation or reduction will be allowed in the run-in phase. Dose modifications of nivolumab are not permitted from the standard dose of 240 mg every 14 days.

The run-in will cease when 4 or more patients have completed chemoradiation and nivolumab therapy at the same nivolumab dose schedule without experiencing grade 3-4 toxicity or other DLT (this will be considered the maximally tolerated dose), or alternatively, if 3/6 patients have experienced grade 3-4 toxicity at dose schedule 3 during administration of adjuvant nivolumab (in which case the entire study will terminate). Therefore, a minimum of 6 patients and a maximum of 18 patients will be enrolled in the run-in phase.

DLT criteria are grade  $\geq 3$  immune-related adverse events, need to hold nivolumab for  $>28$  days due to toxicity, and for patients receiving concurrent nivolumab with chemoradiation, inability to complete chemoradiation or need to hold chemoradiation for  $>3$  days due to immune-related toxicity.

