## **8.4 Analysis Plans**

### **8.4.1 Analysis Population**

Primary endpoint will be determined in patients who receive the study drug for a minimum of 1 cycle (or 14 days) at the MTD schedule.

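### Section 8.4.3 counts death from any cause as an event in both the locoregional control rate and the distant metastasis rate, so both are survival composites, and it gives no read-out time on its day-1 clock

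*Combined protocol and SAP*

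**What the plan says.** The objectives name two rates at a fixed time. Section 2.2 has "To determine the distant metastasis rate at 1 year post-treatment", and section 8.1.2 has "To determine the locoregional control rate at 1 year post-treatment". The Abstract sets both at the same time. Section 2.4.2 lists the endpoint simply as "Distant metastasis rate", and death is part of neither name.

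Section 8.4.3 then defines the analysis. Both durations start on the first day of treatment. Time to distant metastasis ends at "documented clinical or radiographic progression at a distant metastatic site, or death due to any cause". Duration of locoregional control ends at "documented locoregional clinical or radiographic relapse, progression or death due to any cause". For the first it adds: "The Kaplan-Meier analysis will be used to calculate the mean DM rate with 95% confidence interval", and it has a matching sentence for locoregional control. It states no time at which the curve is to be read and plans no estimate that leaves death out of the event.

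**The concern.** A patient who dies without metastasis is reported within the metastasis rate, and a patient who dies with the neck and nasopharynx controlled counts against the control rate. The names promise one quantity and the analysis delivers another. Section 1.1.2 gives weak prevention of distant metastases as a main shortcoming of current care, so readers will look for the metastasis figure and may set it beside metastasis-only figures from other studies. A fatal toxicity without metastasis would appear there as failure of disease control.

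The time is a second gap. Kaplan-Meier gives the probability of remaining event-free at a stated time; a *mean rate* does not say which time. Because the clock starts on day 1 and the objective counts from the end of treatment, the analyst would have to choose the read-out after the data are in.

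**Working it through.** **1. Which patients count as events.** Each row is a patient's course up to the read-out. Progression in the LRC definition is read as locoregional.

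| Course | Metastasis alone | DM per 8.4.3 | Locoregional failure alone | LRC per 8.4.3 |
|---|---|---|---|---|
| Metastasis, alive, locally controlled | event | event | none | none |
| Locoregional failure, alive, no metastasis | none | none | event | event |
| Death with neither | none | event | none | event |
| Death after metastasis, locally controlled | event | event | none | event |

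The named and planned quantities differ wherever a patient dies without the event in question. For LRC this includes deaths that follow metastasis.

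**2. Size.** Let N be the number analysed, m the number with metastasis by time t, and d the number who die without metastasis by t. With no censoring before t:

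- 1 − KM(t) = (m + d)/N
- cumulative incidence of metastasis = m/N
- difference = d/N

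For locoregional control the planned estimate is lower than the control rate by the proportion who die without locoregional failure. The sample sizes come from the plan:

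- N = 40 (section 8.2.1): 1/40 = 2.5 points per death
- N = 28 (section 8.2.4): 1/28 = 3.6 points per death

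The documents give no expected number of such deaths. As an assumed illustration, take N = 40 and m = 4, a metastasis rate of 10%. Then d = 0, 1, 2 or 4 gives a reported figure of 10%, 12.5%, 15% or 20%.

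**3. Where one year after treatment falls.** First, the plan's own duration. Under Dose Schedule 1 the last dose is on day 1 of cycle 12, and cycles last 14 days: 1 + 11 × 14 = day 155, the first day of week 23. This agrees with the 23 weeks in the Abstract. Under Dose Schedules 2 and 3 (section 3.2) the last dose is on day 1 of cycle 11: 1 + 10 × 14 = day 141, the first day of week 21. The Abstract allows up to 33 weeks with delays. Counting from the end of the course:

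| Course | One year post-treatment, from day 1 | Weeks post-treatment at week 52 | Weeks post-treatment at week 75 |
|---|---|---|---|
| 21 weeks | 21 + 52 = week 73 | 31 | 54 |
| 23 weeks | 23 + 52 = week 75 | 29 | 52 |
| 33 weeks | 33 + 52 = week 85 | 19 | 42 |

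The choice matters. Under an assumed constant hazard, an event probability of 15% by week 75 becomes 1 − 0.85^(52/75) = 10.7% if the curve is read at week 52.

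**The case against.** The best defence is that nothing is hidden. Section 8.4.3 states the death component openly, and composites of this kind are legitimate. Counting deaths is also cautious: Table 6.1 schedules imaging only at the end of treatment and at one year after screening, so a death between scans may conceal an undocumented failure. Deaths can be seen elsewhere too, in overall survival and in the adverse-event table for fatal outcomes (section 8.5). The one-year time is not absent from the statistical section, since 8.1.2 gives it.

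Most of this stands, and it supports keeping the composites under accurate names. It does not supply the metastasis and control rates in the objectives, which no section plans to estimate. Nor does 8.1.2 say where its one-year time falls on the day-1 clock in 8.4.3.

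Some stronger readings are tempting but not supported:

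- A reader might infer that the metastasis rate will be materially overstated. The documents give no rate of death without metastasis, and the shift may be zero.
- A reader might infer that the definitions flatter the regimen. Counting deaths makes its figures worse than metastasis-only or control-only figures would be.
- A reader might infer that distant progression counts against locoregional control. Under that heading, locoregional most naturally governs progression as well as relapse, and distant progression is defined separately in the next paragraph. The wording is only slightly loose.
- A reader might infer that every patient who stops early reaches one year post-treatment before week 73. A Dose Schedule 1 patient who stops in week 22 reaches it at week 22 + 52 = 74, and delays push it later.

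**Conclusion.** The point holds as a mismatch between the named endpoints and the planned analysis, with a read-out time left unset. As written, section 8.4.3 yields distant-metastasis-free and locoregional-failure-free survival. The gap from the named rates is the proportion who die without the event before the read-out: about 2.5 points per death at N = 40 and 3.6 at N = 28, assuming no earlier censoring, and nothing if there are no such deaths. The week 73, 75 and 85 figures assume completed courses and count from the end of the course. These are descriptive secondary endpoints. The primary endpoint, its sample size and its decision rule are untouched. The change should be made because it is cheap and prevents a choice of event rule and time point after the data are seen.

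**What to change.** In section 8.4.3:

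- (a) Report the death-inclusive Kaplan-Meier estimates as locoregional-failure-free survival and distant-metastasis-free survival.
- (b) For the named rates, estimate the cumulative incidence of distant metastasis and of locoregional failure, with death without that event as the competing event. Count each type of failure whether or not the other came first. Section 6.1.4 lets follow-up visits end at progression, so later failures would come from the disease status collected under section 6.1.5 and the survival follow-up footnote of Table 6.1.
- (c) Replace the mean rate with the estimate and 95% confidence interval at one pre-specified time from day 1 matched to the planned course, for example week 75 for the 23-week course. State the limit: at week 75 a 21-week course is read 2 weeks after its one-year point, and a 33-week course 10 weeks before it.
- (d) Write locoregional progression in the LRC definition.

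The cost is a few sentences and one standard competing-risk routine on data the plan already provides for. The downside is an extra pair of estimates to report, a read-out time that cannot match every course length exactly, and reliance on telephone or record-based information for some failures after progression.

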#### 8.4.4 Other Analyses/Assessments

Correlative and exploratory analyses will be performed as described in 8.1.3.

### 8.5 Evaluation of Safety

Safety analyses will be performed for all patients having received at least one dose of study drug. The study will use the NCI CTCAE v5.0.

The safety population will consist of all subjects who receive any amount of study treatment. Safety will be assessed by evaluation of AEs. All safety analyses will be performed using the safety population. Adverse event terms recorded on the CRFs will be mapped to preferred terms using the Medical Dictionary for Regulatory Activities (MedDRA). Seriousness, severity grade and relationship to study treatment will be assessed by the investigator. Severity grade will be defined by the National Cancer Institute (NCI) CTCAE v5.0. Listings of AEs will be provided.

Separate tables will present the following by dose group and study phase:

- All treatment-emergent AEs
- Treatment-emergent AEs by CTCAE grade
- Grade 3 or greater treatment-emergent AEs
- Treatment-related, treatment-emergent AEs
- Dose-limiting toxicity AEs
- Serious treatment-emergent AEs
- Treatment-emergent AEs with an outcome of death
- Treatment-emergent AEs leading to discontinuation of nivolumab.
- Treatment-emergent AEs resulting in interruption or reduction or delay of nivolumab.

### 8.6 Study Results

Study results will be submitted to drug manufacturer (BMS), as well as presented at national or international oncology conferences, and published in peer-reviewed scientific journals.

## 9 Study Management

### 9.1 Pre-study Documentation

This study will be conducted in accordance with the ethical principles that have their origin in the Declaration of Helsinki as stated in 21 CFR §312.120(c)(4); consistent with Good Clinical Practice (GCP), as defined by the International Conference on Harmonisation (ICH), WHO and local directives including all applicable regulatory requirements.

The protocol, any amendments, and the subject informed consent will receive Institutional Review Board/Independent Ethics Committee (IRB/IEC) approval before initiation of the study. Before initiating this trial, the Investigator will have written and dated approval from the Institutional Review Board for the protocol, written informed consent form, subject recruitment materials, and any other written information to be provided to subjects before any protocol related procedures are performed on any subjects.

The clinical investigation will not begin until either FDA has determined that the study under the Investigational Drug Application (IND) is allowed to proceed or the Investigator has received a letter from FDA stating that the study is exempt from IND requirements.

The Investigator must comply with the applicable regulations in Title 21 of the Code of Federal Regulations (21 CFR §50, §54, and §312), GCP/ICH guidelines, and all applicable regulatory requirements. The IRB must comply with the regulations in 21 CFR §56 and applicable regulatory requirements.

### 9.2 Institutional Review Board Approval

The protocol, the proposed informed consent form, and all forms of participant information related to the study (e.g. advertisements used to recruit participants) will be reviewed and approved by the UCSF Institutional Review Board. Prior to obtaining IRB approval, the protocol must be approved by the Helen Diller Family Comprehensive Cancer Center Site Committee and by the Protocol Review Committee (PRC). The initial protocol and all protocol amendments must be approved by the IRB prior to implementation.

### 9.3 Informed Consent

All participants must be provided a consent form describing the study with sufficient information for each participant to make an informed decision regarding their participation. Participants must sign the IRB-approved informed consent form prior to participation in any study specific procedure. The participant must receive a copy of the signed and dated consent document. The original signed copy of the consent document must be retained in the medical record or research file.

Informed consent will be obtained by personnel who are qualified by education, training, and experience to perform their respective tasks and that the study will not use the services of study personnel for whom sanctions have been invoked or where there has been scientific misconduct or fraud. Signed, dated Informed Consent will be obtained from each of the participants. Investigators will ensure that subjects--or, in those situations where consent cannot be given by subjects, their legally acceptable representatives--are clearly and fully informed about the purpose, potential risks, and other critical issues regarding clinical studies in which they volunteer to participate. The approved informed consent form will adhere to the ethical principles that have their origin in the Declaration of Helsinki. The informed consent will include

relevant safety information regarding dose/schedule of investigational products and any other drugs/procedures. BMS and health authorities will have direct access to study records. The informed consent will disclose BMS support of the study (e.g., study drug, funding).

#### **9.4 Changes in the Protocol**

Once the protocol has been approved by the UCSF IRB, any changes to the protocol must be documented in the form of an amendment. The amendment must be signed by the Investigator and approved by PRC and the IRB prior to implementation.

If it becomes necessary to alter the protocol to eliminate an immediate hazard to patients, an amendment may be implemented prior to IRB approval. In this circumstance, however, the Investigator must then notify the IRB in writing within five (5) working days after implementation. The Study Chair and the UCSF study team will be responsible for updating any participating sites.

#### **9.5 Handling and Documentation of Clinical Supplies**

The UCSF Principal Investigator and each participating site will maintain complete records showing the receipt, dispensation, return, or other disposition of all investigational drugs. The date, quantity and batch or code number of the drug, and the identification of patients to whom study drug has been dispensed by patient number and initials will be included. The sponsor-investigator will maintain written records of any disposition of the study drug.

The Principal Investigator shall not make the investigational drug available to any individuals other than to qualified study patients. Furthermore, the Principal Investigator will not allow the investigational drug to be used in any manner other than that specified in this protocol.

#### **9.6 Case Report Forms (CRFs)**

The Principal Investigator and/or his/her designee, will prepare and maintain adequate and accurate participant case histories with observations and data pertinent to the study. Study specific Case Report Forms (CRFs) will document safety and treatment outcomes for safety monitoring and data analysis. All study data will be entered into OnCore® via standardized CRFs in accordance with the CTMS study calendar, using single data entry with a secure access account. The Clinical Research Coordinator (CRC) will complete the CRFs as soon as possible upon completion of the study visit; the Investigator will review and approve the completed CRFs.

The information collected on CRFs shall be identical to that appearing in original source documents. Source documents will be found in the patient's medical records maintained by UCSF personnel. All source documentation should be kept in separate research folders for each patient.

In accordance with federal regulations, the Investigator is responsible for the accuracy and authenticity of all clinical and laboratory data entered onto CRFs. The PI will approve all completed CRFs to attest that the information contained on the CRFs is true and accurate.

All source documentation and CTMS data will be available for review/monitoring by the UCSF DSMC and regulatory agencies.

The Principal Investigator will be responsible for ensuring the accurate capture of study data. At study completion, when the CRFs have been declared to be complete and accurate, the database will be locked. Any changes to the data entered into the CRFs after that time can only be made by joint written agreement among the Study Chair, the Trial Statistician, and the Protocol Project Manager.

## 9.7 Oversight and Monitoring Plan

The UCSF Helen Diller Family Comprehensive Cancer Center DSMC will be the monitoring entity for this study. The UCSF DSMC will monitor the study in accordance with the NCI-approved Data and Safety Monitoring Plan (DSMP). The DSMC will routinely review all adverse events and suspected adverse reactions considered "serious". The DSMC will audit study-related activities to ensure that the study is conducted in accordance with the protocol, local standard operating procedures, FDA regulations, and Good Clinical Practice (GCP). Significant results of the DSMC audit will be communicated to the IRB and the appropriate regulatory authorities at the time of continuing review, or in an expedited fashion, as applicable. See Appendix 2 Data and Safety Monitoring Plan for a Multicenter Institutional Study (For Run-In Phase) and Data and Safety Monitoring Plan for Multicenter Institutional Study (Phase 2 or 3 Institutional Study) – For Dose Expansion Phase for additional information.

